5.2.5 Other safety parameters

Not applicable

5.2.6 Assessment of adverse events

5.2.6.1 Definitions of adverse events

5.2.6.1.1 Adverse event

An adverse event (AE) is defined as any untoward medical occurrence in a patient or clinical investigation subject administered a medicinal product and which does not necessarily have to have a causal relationship with this treatment.

An AE can therefore be any unfavourable and unintended sign (including an abnormal laboratory finding), symptom, or disease temporally associated with the use of a medicinal product, whether considered related or not.

The following should also be recorded as an AE in the CRF and BI SAE form (if applicable):

- Worsening of the underlying disease or of other pre-existing conditions
- Changes in vital signs, ECG, physical examination, and laboratory test results, if they are judged clinically relevant by the investigator

If such abnormalities already pre-exist prior to trial inclusion, they will be considered as baseline conditions and should be collected in the eCRF only.

5.2.6.1.2 Serious adverse event

A serious adverse event (SAE) is defined as any AE which fulfils at least one of the following criteria:

- Results in death
- Is life-threatening, which refers to an event in which the patient was at risk of death at the time of the event; it does not refer to an event that hypothetically might have caused death if more severe
- Requires inpatient hospitalisation, or prolongation of existing hospitalisation

Proprietary confidential information © 2023 Boehringer Ingelheim International GmbH or one or more of its affiliated companies

- Results in persistent or significant disability or incapacity
- Is a congenital anomaly/birth defect
- Is deemed serious for any other reason if it is an important medical event when based upon appropriate medical judgment which may jeopardise the patient and may require medical or surgical intervention to prevent one of the other outcomes listed in the above definitions. Examples of such events are intensive treatment in an emergency room or at home for allergic bronchospasm, blood dyscrasias or convulsions that do not result in hospitalisation or development of dependency or abuse

5.2.6.1.3 AEs considered ‘Always Serious’

In accordance with the European Medicines Agency initiative on Important Medical Events, Boehringer Ingelheim has set up a list of AEs, which, by their nature, can always be considered to be ‘serious’ even though they may not have met the criteria of an SAE as defined above.

The latest list of ‘Always Serious AEs’ can be found in the eDC system, an electronic data capture system which allows the entry of trial data at the trial site. A copy of the latest list of ‘Always Serious AEs’ will be provided upon request. These events should always be reported as SAEs as described in Section [5.2.6.2](#).

Cancers of new histology must be classified as a serious event regardless of the time since discontinuation of the trial medication and must be reported as described in Section [5.2.6.2](#), subsections ‘AE Collection’ and ‘AE reporting to sponsor and timelines’.

5.2.6.1.4 Adverse events of special interest

The term adverse events of special interest (AESI) relates to any specific AE that has been identified at the project level as being of particular concern for prospective safety monitoring and safety assessment within this trial, e.g. the potential for AEs based on knowledge from other compounds in the same class. AESIs need to be reported to the sponsor’s Pharmacovigilance Department within the same timeframe that applies to SAEs, please see Section [5.2.6.2.2](#).

The following are considered as AESIs:

- Potential severe DILI
A potential severe Drug Induced Liver Injury (DILI) that requires follow-up is defined by the following alterations of hepatic laboratory parameters:
 - o An elevation of AST (aspartate aminotransferase) and/or ALT (alanine aminotransferase) ≥ 3 -fold ULN combined with an elevation of total bilirubin ≥ 2 -fold ULN measured in the same blood sample, or in samples drawn within 30 days of each other, or
 - o Aminotransferase (ALT, and/or AST) elevations ≥ 10 -fold ULN

These lab findings constitute a hepatic injury alert and the subjects showing these lab abnormalities need to be followed up according to the ‘DILI checklist’ provided in the

Proprietary confidential information © 2023 Boehringer Ingelheim International GmbH or one or more of its affiliated companies

ISF. In case of clinical symptoms of hepatic injury (icterus, unexplained encephalopathy, unexplained coagulopathy, right upper quadrant abdominal pain, etc.) without lab results (ALT, AST, total bilirubin) available, the Investigator should make sure that these parameters are analysed, if necessary in an unscheduled blood test. Should the results meet the criteria of hepatic injury alert, the procedures described in the DILI checklist should be followed.

5.2.6.1.5 Intensity (severity) of AEs

The intensity (severity) of the AE should be judged based on the following:

Mild: Awareness of sign(s) or symptom(s) that is/are easily tolerated

Moderate: Sufficient discomfort to cause interference with usual activity

Severe: Incapacitating or causing inability to work or to perform usual activities

5.2.6.1.6 Causal relationship of AEs

Medical judgment should be used to determine whether there is a reasonable possibility of a causal relationship between the AE and the given trial treatment, considering all relevant factors, including pattern of reaction, temporal relationship, de-challenge or re-challenge, confounding factors such as concomitant medication, concomitant diseases and relevant history.

Arguments that may suggest that there is a reasonable possibility of a causal relationship could be:

- The event is consistent with the known pharmacology of the drug
- The event is known to be caused by or attributed to the drug class
- A plausible time to onset of the event relative to the time of drug exposure
- Evidence that the event is reproducible when the drug is re-introduced
- No medically sound alternative aetiologies that could explain the event (e.g. pre-existing or concomitant diseases, or co-medications)
- The event is typically drug-related and infrequent in the general population not exposed to drugs (e.g. Stevens-Johnson syndrome)
- An indication of dose-response (i.e. greater effect size if the dose is increased, smaller effect size if dose is reduced)

Arguments that may suggest that there is no reasonable possibility of a causal relationship could be:

- No plausible time to onset of the event relative to the time of drug exposure is evident (e.g. pre-treatment cases, diagnosis of cancer or chronic disease within days / weeks of drug administration; an allergic reaction weeks after discontinuation of the drug concerned)
- Continuation of the event despite the withdrawal of the medication, taking into account the pharmacological properties of the compound (e.g. after 5 half-lives). Of note, this criterion may not be applicable to events whose time course is prolonged despite removing the original trigger

Proprietary confidential information © 2023 Boehringer Ingelheim International GmbH or one or more of its affiliated companies

- There is an alternative explanation (e.g. situations where other drugs or underlying diseases appear to provide a more likely explanation for the observed event than the drug concerned)
- Disappearance of the event even though the trial drug treatment continues or remains unchanged

5.2.6.2 Adverse event collection and reporting

5.2.6.2.1 AE collection

Upon enrolment into a trial, the subject's baseline condition is assessed (for instance, by documentation of medical history/concomitant diagnoses), and relevant changes from baseline are noted subsequently.

Subjects will be required to report spontaneously any AEs. In addition, each subject will be regularly assessed by the medical staff throughout the clinical trial and whenever the investigator deems necessary. As a minimum, subjects will be questioned for AEs (and concomitant therapies) at the time points indicated in the [Flow Chart](#). Assessment will be made using non-specific questions such as 'How do you feel?'. Specific questions will be asked wherever necessary in order to more precisely describe an AE.

A carefully written record of all AEs shall be kept by the investigator in charge of the trial. Records of AEs shall include data on the time of onset, end time, intensity of the event, and any treatment or action required for the event and its outcome.

The following must be collected and documented on the appropriate CRFs by the investigator:

- From signing the informed consent onwards until an individual subject's end of trial (the End of Study (EoS) visit):
 - All AEs (serious and non-serious) and all AESIs
 - The only exception to this rule are AEs (serious and non-serious) and AESIs in Phase I trials in healthy volunteers, when subjects discontinue from the trial due to screening failures prior to administration of any trial medication. In these cases, the subjects' data must be collected at trial site but will not be entered in the CRF and will not be reported in the CTR.
- After the individual subject's end of trial:
 - The investigator does not need to actively monitor the subject for new AEs but should only report any occurrence of cancer and trial treatment related SAEs and trial treatment related AESIs of which the investigator may become aware of by any means of communication, e.g. phone call. Those AEs should be reported on the BI SAE form (see Section [5.2.6.2.2](#)), but not on the CRF.

Proprietary confidential information © 2023 Boehringer Ingelheim International GmbH or one or more of its affiliated companies

5.2.6.2.2 AE reporting to the sponsor and timelines

The Investigator must report SAEs, AESIs, and non-serious AEs which are relevant for the reported SAE or AESI, on the BI SAE form to the sponsor's unique entry point within 24 hours of becoming aware of the event, the country specific reporting process will be provided in the ISF. The same timeline applies if follow-up information becomes available. On specific occasions, the Investigator could inform the sponsor upfront via telephone. This does not replace the requirement to complete and send the BI SAE form.

With receipt of any further information to these events, a follow-up SAE form has to be provided. For follow-up information, the same rules and timeline apply as for initial information. All (S)AEs, including those persisting after the individual subject's end of trial, must be followed up until they have resolved, have been sufficiently characterized (e.g. as 'chronic' or 'stable'), or no further information can be obtained.

5.2.6.2.3 Pregnancy

If a partner of a male trial participant becomes pregnant, potential drug exposure during pregnancy must be reported immediately (without undue delay) by means of Part A of the Pregnancy Monitoring Form to the sponsor's unique entry point. This requires written consent of a pregnant partner. Reporting and consenting must be in line with local regulations. The ISF will contain the trial specific information and consent for the pregnant partner.

The outcome of the pregnancy associated with the drug exposure during pregnancy must be followed up and reported to the sponsor's unique entry point on the Pregnancy Monitoring Form for Clinical Studies (Part B). The ISF will contain the Pregnancy Monitoring Form for Clinical Studies (Part A and Part B).

As pregnancy itself is not to be reported as an AE, in the absence of an accompanying SAE and/or AESI, only the Pregnancy Monitoring Form for Clinical Studies and not the SAE form is to be completed. If there is an SAE and/or AESI associated with the pregnancy, an SAE form must be completed in addition.

5.3 DRUG CONCENTRATION MEASUREMENTS AND PHARMACOKINETICS

5.3.1 Assessment of pharmacokinetics

For the assessment of pharmacokinetics, blood and urine samples will be collected at the time points / time intervals indicated in the [Flow Chart](#). The actual sampling times will be recorded and used for determination of pharmacokinetic parameters.

5.3.2 Methods of sample collection

5.3.2.1 Sampling of whole blood and plasma

Whole blood and plasma will be collected at time points shown in the [Flow Chart](#):

- To determine total [¹⁴C]-radioactivity concentrations in whole blood and plasma

Proprietary confidential information © 2023 Boehringer Ingelheim International GmbH or one or more of its affiliated companies

- To determine concentrations of BI 1291583 and its metabolites M407(1) / BI 1373234, M396(1) / CD 18507, M397(1) / CD 17849, M549(1) / CD 16785 and M141(1) / CD 16426 in plasma
- To identify additional metabolites of BI 1291583 in plasma (to be reported separately)
- To determine the blood cell/plasma and blood/plasma ratios of [¹⁴C]-radioactivity

5.3.2.1.1 Sampling of whole blood and plasma for [¹⁴C]-radioactivity

For quantification of concentrations of [¹⁴C]-radioactivity in whole blood and plasma, blood will be drawn by means of two separate blood collection tubes from an antecubital or forearm vein into an K₂-EDTA (dipotassium ethylenediaminetetraacetic acid)-anticoagulant blood drawing tube at the times indicated in the [Flow Chart](#). Blood will be withdrawn by means of either an indwelling venous catheter or by venipuncture with a metal needle. Afterwards, separate aliquots of whole blood and plasma will be prepared for total radioactivity analysis.

For a detailed description of sample volume, sample handling, sample preparation, sample storage, tube labelling and sample shipment, refer to the laboratory manual.

5.3.2.1.2 Quantification of BI 1291583 and its metabolites in plasma

For quantification of concentrations BI 1291583 and its metabolites [REDACTED]

in plasma, blood will be drawn from an antecubital or forearm vein into an K₂-EDTA (dipotassium ethylenediaminetetraacetic acid)-anticoagulant blood drawing tube at the times indicated in the [Flow Chart](#). Blood will be withdrawn by means of either an indwelling venous catheter or by venipuncture with a metal needle.

For a detailed description of sample volume, sample handling, sample preparation, sample storage, tube labelling and sample shipment, refer to the laboratory manual.

5.3.2.1.3 Sampling of plasma for metabolic profiling and structural elucidation

At each time point listed in the [Flow Chart](#) for metabolic profiling sampling, full blood will be withdrawn from an antecubital or forearm vein into two K₂-EDTA (dipotassium ethylenediaminetetraacetic acid)-anticoagulant blood drawing tube. The blood samples will be processed in the same way as the PK samples (see laboratory manual). However, the obtained plasma from one of the samples will be divided into two aliquots both to be used for metabolic profiling via AMS analysis. The other plasma sample is used for further internal investigations of BI 1291583 metabolism in the drug metabolism laboratory of BI.

Evaluation of drug metabolism will be reported separately and will not be included in the CTR.

For detailed description of sample volume, sample handling, sample preparation, sample storage, tube labelling and sample shipment refer to the laboratory manual.

5.3.2.2 Sampling of urine

Urine will be collected at time points or in intervals as indicated in the [Flow Chart](#):

Proprietary confidential information © 2023 Boehringer Ingelheim International GmbH or one or more of its affiliated companies

- To determine total [¹⁴C]-radioactivity
- To determine concentrations of BI 1291583
- To investigate the metabolic profiling of BI 1291583 (to be reported separately)

A blank sample will be taken within approximately 14 hours prior to drug administration.

The weight of the containers has to be determined prior to (empty containers) and at the end of the collection interval. The urine volume (weight will be set equal to volume, i.e. 1 kg = 1 L, without correction for specific gravity of urine) for each collection interval will be documented. Volunteers will be asked to empty their bladders at the end of each sampling interval. The exact start and end times of the urine collection intervals will be recorded in the CRF.

All urine samples after administration of BI 1291583 (C-14) until release criteria are met are planned to be used for determination of [¹⁴C]-radioactivity as well as for analysis of BI 1291583. Samples for metabolic profiling will be selected according to the levels of radioactivity in each urine sample.

For a detailed description of preparation of collection containers, sample additives, sample storage, sample handling, labelling, and sample shipment refer to the laboratory manual.

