2.1.2 Primary endpoints

Primary endpoints will be the mass balance and total recovery of [¹⁴C]-radioactivity in urine and faeces:

[figure not shown]
- $fe_{urine, 0-tz}$ (fraction of [¹⁴C]-radioactivity excreted in urine expressed as percentage of the administered dose over the time interval from 0 to the last quantifiable time point)
- $fe_{faeces, 0-tz}$ (fraction of [¹⁴C]-radioactivity excreted in faeces expressed as percentage of the administered dose over the time interval from 0 to the last quantifiable time point)

Timeframe: The timeframe for determination of these endpoints depends on individual excretion/ recovery of radioactivity and may vary between 2 and 6 weeks, inclusive, after drug administration.

[figure not shown]

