3. DESCRIPTION OF DESIGN AND TRIAL POPULATION

3.1 OVERALL TRIAL DESIGN

The trial will be performed as an open-label, single-arm, single-dose trial in healthy male subjects to investigate the basic pharmacokinetics of BI 1291583, its metabolites (M407[1] / BI 1373234, M396(1) / CD 18507, M397(1) / CD 17849, M549(1) / CD 16785 and M141(1) / CD 16426) and [¹⁴C]-radioactivity, including mass balance, excretion pathways and metabolism following a single oral dose of [REDACTED] BI 1291583 (C-14).

A total of 8 healthy male subjects are planned to participate in the trial.

The planned radioactive dose per subject is approximately ≈ 0.36 MBq (0.04 mSv).

On Day 1, subjects will receive the drug product, i.e. [REDACTED] BI 1291583 (C-14) and will then stay in the study centre up to the morning of Day 15 for collection of samples of blood, urine and faeces, and if applicable for collection of vomit (within 24 hours after drug administration).

[REDACTED]

Subjects will be readmitted to the study centre for 24 h collection intervals of urine and faeces on Days 21, 28, 35, and 42, if release criteria have not been met before. Within 24 hours before each of these once-weekly in-house collection intervals, subjects are to collect faeces at home. This 24-h interval home collection faeces will be used for analysis in case no defecation occurs in the subsequent 24 h in-house collection interval. Otherwise it will be discarded.

For determination of whether release criteria have been reached for individual subjects, [¹⁴C]-radioactivity will be measured in excreta (urine, faeces), and vomit, if applicable. The actual recovery results will be reported as a percentage of the administered dose.

If the following release criteria have been met, the subsequent 24 h collection intervals after Day 15 will not be performed:

- Greater than or equal to 90% of the administered [¹⁴C] dose has been recovered in urine and faeces combined over the investigational period

and

- If <1% of the [¹⁴C] dose administered has been collected in urine and faeces within 2 separate, consecutive 24-h intervals

Note:

For calculation of release criteria during clinical conduct the fraction of administered [¹⁴C] dose will be rather underestimated as it will be based on the available samples, only. For the final analysis, the total excreted [¹⁴C]-radioactivity will be derived including an interpolation method to account for the time periods without samples taken (see Section [7.2.2](#)).

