3.2 DISCUSSION OF TRIAL DESIGN, INCLUDING THE CHOICE OF CONTROL GROUP

This is a well-known design for a [¹⁴C] human study for investigation of absorption, metabolism, and excretion including determination of mass balance. Inclusion of a control group is not required for this investigation. The study will use a low amount of [¹⁴C]-radioactivity and accelerator mass spectrometry (AMS) for the measurement of [¹⁴C] for sensitive detection, tracking and quantification of the parent drug and metabolites of mass balance.

Based on excretion data of drug-related radioactivity in the rat ADME trial [[n00256437](#), [n00258671](#)] and the available PK data from clinical trials (see Section [1.2.1.2](#)) a prolonged sampling duration was planned.

Following 15 days in-house excreta collection after dosing, subjects will return on a weekly basis **for in-house 24-h collection intervals (urine/faeces)** for up to 6 weeks (i.e., up to Day 43) after dosing **as long as release criteria are not met** (Section [3.1](#)).

Blinding and randomisation is not necessary because all subjects receive the same treatment. Furthermore, the main endpoints cannot be subjectively influenced as they are determined in urine, faecal and blood samples.

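### Urine weight is recorded as volume with no density correction and the assay basis is unstated; if urine radioactivity is measured per mL, fe_urine,0-tz is overstated by about 0.5–3% of its value (assumed density 1.005–1.030 kg/L)

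*Protocol*

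**What the plan says.** Protocol 5.3.2.2 describes how the urine quantity is obtained: "The weight of the containers has to be determined prior to (empty containers) and at the end of the collection interval". The resulting weight is then converted to a volume: "weight will be set equal to volume, i.e. 1 kg = 1 L, without correction for specific gravity of urine". That volume is what is documented for each collection interval. Post-dose urine samples up to release "are planned to be used for determination of [¹⁴C]-radioactivity as well as for analysis of BI 1291583".

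The endpoint that depends on this is fe_urine,0-tz, defined in protocol 2.1.2 as the "fraction of [¹⁴C]-radioactivity excreted in urine expressed as percentage of the administered dose over the time interval from 0 to the last quantifiable time point". Urine recovery also enters the first release criterion in protocol 3.1: "Greater than or equal to 90% of the administered [¹⁴C] dose has been recovered in urine and faeces combined over the investigational period". The second criterion there requires less than 1% of dose in urine and faeces within two separate, consecutive 24-h intervals.

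The unit of the urine radioactivity result is not stated. Protocol 3.2 names the technique, "accelerator mass spectrometry (AMS) for the measurement of [¹⁴C] for sensitive detection, tracking and quantification of the parent drug and metabolites of mass balance", without a unit. For the remaining detail, 5.3.2.2 says that for "sample additives, sample storage, sample handling, labelling, and sample shipment refer to the laboratory manual". Protocol 7.2.2 leaves the endpoint calculation to the sponsor's internal procedures. SAP 7.4.1 repeats the interpolation rule and adds no density correction.

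**The concern.** An excreted amount is a concentration times a quantity of urine, and the two must be on the same basis. A concentration per mL needs a true volume; a concentration per gram needs a weight. The protocol weighs the urine and then relabels the weight as a volume. If the laboratory reports per mL, the product is too large by the density of the urine.

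The text gives some reason to think a per-volume calculation is intended. Faeces (5.3.2.3) and vomit (5.3.2.4) are left as weights, and only urine is turned into a volume. A documented volume is mainly useful when it is multiplied by a concentration per volume. This is an inference, not a statement in the documents.

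At stake is the accuracy of one of the two primary endpoints. The error falls on the urine side only, so it would move the split between urine and faeces as well as total recovery.

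**Working it through.** The plan has no figure to reproduce: it gives no density, no assay unit and no formula for fe_urine.

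**Inputs**
- Net urine weight W in each interval (protocol 5.3.2.2).
- Recorded volume = W, at 1 kg = 1 L (protocol 5.3.2.2).
- Urine density ρ: not in the documents. Assumed 1.005–1.030 kg/L.
- fe_urine: no value in the documents. Assumed 20%, 40% and 60% of dose for illustration.

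**Step 1: one interval.** If concentration C is per mL, the true amount is C × W/ρ and the plan's amount is C × W. The ratio is ρ, so the relative error is ρ − 1 and the error in points of dose is fe_true × (ρ − 1). If C is per gram, the amount is C × W and the error is exactly zero.

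| Density (kg/L) | Relative error | fe 20% | fe 40% | fe 60% |
|---|---|---|---|---|
| 1.000 | 0 | 0 | 0 | 0 |
| 1.005 | +0.5% | +0.1 | +0.2 | +0.3 |
| 1.010 | +1.0% | +0.2 | +0.4 | +0.6 |
| 1.020 | +2.0% | +0.4 | +0.8 | +1.2 |
| 1.030 | +3.0% | +0.6 | +1.2 | +1.8 |

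A wider assumed range of 1.003–1.035 gives +0.3% to +3.5%. At 0.999 the error is −0.1%.

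**Step 2: all intervals together.** Let A_i be the true amount in interval i. The recorded total over the true total is Σ(ρ_i A_i) / Σ A_i, an amount-weighted mean of the densities. With 17 in-house intervals of equal amount, all at 1.020, it is (17 × 1.020)/17 = 1.020, the same as for one interval. The relative error therefore does not build up. Linear interpolation across the unsampled weeks (protocol 7.2.2) is linear in the observed amounts, so it carries the factor forward without enlarging it.

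**Step 3: release, first condition.** With urinary share s of true recovery, recorded total = true total × [1 + s(ρ − 1)]. At s = 0.5 (assumed), a recorded 90% corresponds to a true total of:
- 90/1.0025 = 89.8% at ρ = 1.005
- 90/1.010 = 89.1% at ρ = 1.020
- 90/1.015 = 88.7% at ρ = 1.030

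The condition becomes slightly easier to meet.

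**Step 4: release, second condition.** If a day's excretion were entirely urinary at ρ = 1.030, a recorded value below 1% would need a true value below 1/1.030 = 0.971%. A true 0.98% would be recorded as 0.98 × 1.030 = 1.01% and would fail. The condition becomes slightly harder to meet. Both conditions are required, so the net direction depends on which one binds for the subject.

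**The case against.** The strongest objection is that no bias has been shown. The assay unit may be per gram, in which case the conversion does no harm to fe_urine. The details sit in the laboratory manual and internal procedures, which are not among the documents. This stands, and it is why the point is conditional. What remains is that the basis of a primary endpoint is not stated where the conversion rule is.

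A second objection is that the simplification is openly disclosed, the analysis is descriptive (protocol 7.1), and no power calculation was made (7.5). This also stands: no test or sample size is affected, and no conclusion about the route of elimination has been shown to change. However, SAP section 7 reports PK parameters to three significant digits, and at ρ = 1.020 a true 40.0% would appear as 40.8%.

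Three stronger readings are tempting, and the documents do not support them:
- **Every interval in every subject is overstated.** This needs density above 1 kg/L in every container, and no density is given. Protocol 4.1.4 and 4.2.2.2 provide about 240 mL of water with the dose and 240 mL more at 2 h and at 4 h, so very dilute early urine with an error near zero is plausible (assumption). Intervals without quantifiable radioactivity add nothing.
- **The error accumulates over the collection period.** Step 2 shows that the relative error does not.
- **Subjects are pushed towards early release.** This considers only the 90% condition. The second condition moves the other way. Protocol 3.1 also notes that recovery during conduct is understated because it rests on available samples only. That opposes the inflation in the weekly phase but offers little offset at Day 15, when collection has been continuous.

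**Conclusion.** The point holds as a small, conditional one. If urine [14C]-radioactivity is measured per mL, fe_urine,0-tz is overstated by the amount-weighted urine density wherever that exceeds 1 kg/L. The size is about 0.5–3% relative for an assumed density of 1.005–1.030, or 0.2–1.2 percentage points of dose at an assumed fe_urine of 40%. If measurement is per gram, it is zero. Density, urinary fraction and assay basis are all assumptions, because the documents give none of them. When density exceeds 1 kg/L the error has one sign, so averaging over 8 subjects does not reduce it. Release could be affected only for a subject close to one of the two thresholds, in a direction that cannot be stated in general. This is a cheap improvement to a primary endpoint, not a flaw that threatens the trial's conclusions.

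**What to change.** In protocol 5.3.2.2, for radioactivity, replace the weight-to-volume rule with: *Urine [14C]-radioactivity is determined on weighed aliquots and expressed per gram; the amount excreted is activity per gram times net urine weight.* The laboratory manual should say the same. It should also say whether any additive is included in the tare, since the weight used must be that of the material from which the aliquot is drawn.

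The containers are already weighed empty and at the end of each interval, so no extra sample or subject burden arises. The cost is one weighing step per aliquot at the laboratory, if this is not already done, plus the sentence above. If the laboratory already reports per gram, stating so is enough.

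Converting weight to volume by measured density for the parent-drug concentrations is optional and not needed for the primary endpoints. A specific-gravity reading would be a new measurement, because the urinalysis panel in Table 5.2.3: 1 does not include one.
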